5.5 Discontinuation and Withdrawal

Participants are free to discontinue their participation in the study at any time, without prejudice to further treatment. Participants who discontinue from the study will always be asked about the reason(s) for their discontinuation and about the presence of any adverse events. If possible, they will be seen and assessed by an

Investigator and complete the withdrawal of informed consent procedure (see Appendix B; PICF). Where participants are not willing to continue any research assessments, they will be considered withdrawn from the study. Adverse events will be followed up until resolution, the adverse event stabilises, or the participant is lost to follow up.

Participant discontinuation criteria

Participants will be discontinued from participating in the study in the following circumstances and, if in need, be referred to their primary medical officer

1. Participants who develop any complications during the study
2. Participants who become too vulnerable or fragile during the study
3. Participants who miss more than 3 weeks of the treatment sessions
4. Participants who do not have a treating team

Discontinuation of parts of this study or the entire study will be considered if new information about reconsolidation therapy becomes known to the researchers.

Escalation procedure

If a participant develops a known (or previously undocumented) adverse reaction to the treatment during the study, clinical and research staff will refer to the *Recognising and Responding to Physiological deterioration SOP* which will include some or all of the following:

- Appropriate and timely medical care is provided by trained and qualified staff. If required, the emergency services (Queensland Ambulance Services – QSA) and UniSC security are contacted immediately.
- Attending registered nurse will monitor physiological signs and symptoms on initial session.
- If the ambulance service is not required, the participant will be referred for consultation with their GP and their participation from the study will be withdrawn.
- If the ambulance service is required for immediate medical admission, the clinical and research staff will supply relevant patient information to assist with participant treatment and monitoring.

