5.6 Safety Measures

The TI/NPRC has Standard Operating Procedures (SOP) in place to manage adverse and severe adverse events, complaints and feedback and medical emergencies. The PI is required to ensure all study staff are aware of the definitions and procedures in the SOP. Summary details of the SOP can be found in Appendix I.

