The anti-anginal activity of propranolol hydrochloride likely stems from a reduction in left ventricular work and oxygen utilization due to the inhibition of cardiac sympathetic nerve stimulation. Propranolol hydrochloride has also demonstrated serotonin antagonism, though the therapeutic benefit of this property in centrally mediated disorders is still uncertain. As with other β -adrenoreceptor blocking agents, propranolol hydrochloride has negative inotropic effects, and therefore, it is contraindicated in patients with congestive heart failure.

Known adverse events

Propranolol hydrochloride is usually well tolerated, and side effects are transient in nature, rarely necessitating withdrawal of treatment. The most serious adverse reactions encountered are congestive heart failure and bronchospasm in susceptible patients. Common adverse reactions include fatigue and/or lassitude (often transient), bradycardia, cold extremities and exacerbation of Raynaud's phenomenon, sleep disturbances including vivid dreams/nightmares. Other less frequently reported adverse reactions include gastrointestinal disturbances (nausea, vomiting, diarrhoea, abdominal pain), congestive heart failure, dizziness, bronchospasm. Rare cases of thrombocytopenia and purpura have been reported. CNS symptoms including mood changes and hallucinations have been reported rarely. It should be noted that those symptoms have been reported among individuals taking propranolol every day for prolonged periods of time. Our study participants will be taking propranolol once a week, for 6 weeks.

Known contraindications or warnings:

- **Cardiovascular:**
 - o Congestive heart failure
 - o Right ventricular failure secondary to pulmonary hypertension
 - o Significant right ventricular hypertrophy
 - o Sick sinus syndrome
 - o Sinus bradycardia (less than 45 to 50 beats/minute)
 - o Second- and third-degree A-V block
 - o Hypotension
 - o Severe peripheral arterial circulatory disturbances
 - o Prinzmetal's angina
- **Hypoglycaemia, prolonged fasting and metabolic acidosis:**
 - o Propranolol must not be used in patients prone to hypoglycaemia, i.e. patients after prolonged fasting or patients with restricted counter regulatory reserves. In metabolic acidosis (e.g., in diabetes), the premonitory signs of hypoglycaemia may be masked in patients receiving hypoglycaemic agents.
- **Asthma/bronchospasm:**

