 - o β -adrenergic blockade of the smooth muscle of bronchi and bronchioles may result in an increased airways resistance. These drugs also reduce the effectiveness of asthma treatment. This may be dangerous in susceptible patients. Therefore β -blockers are contraindicated in any patient with a history of bronchial asthma, airways obstruction or a tendency to bronchospasm. Use of

cardioselective β -blockers can also result in severe bronchospasm. If such therapy must be used, great caution should be exercised. Alternative therapy should be considered.

- **Other:**
 - o Allergic disorders (including allergic rhinitis) which may suggest a predisposition to asthma or bronchospasm
 - o Shock (including cardiogenic and hypovolaemic shock)
 - o Hypersensitivity to the drug
 - o Anaesthesia with agents that produce myocardial depression (e.g., ether, chloroform)
 - o Untreated pheochromocytoma

Pharmacokinetics

- o **Absorption:** Studies with propranolol hydrochloride in humans indicate that it is almost completely absorbed from the intestine. A large part of the absorbed drug is lost to systemic circulation due to the first pass metabolism in the liver. After repeated administration, the first pass removal process becomes saturated and, at steady state, the plasma concentration is proportional to the dose, although there is some variation between patients as to the blood levels achieved at a given dose. In addition, correlation of plasma level to therapeutic effect varies considerably with propranolol as with some other β -blockers. Blood level measurements show that after intravenous administration, the concentration in the circulation decreases rapidly due mainly to uptake by tissues generally.
- o **Bioavailability:** In general, the peak blood level occurs between 1 and 3 hours after oral administration and will have an average value of 0.1 $\mu\text{g}/\text{mL}$ per 80 mg single dose. The peak blood level is proportional to the dose. With chronic administration the mean plasma half-life is from 3 to 6 hours, determined by clearance and plasma binding. Following intravenous administration, the plasma half-life of propranolol is about 2 hours and the ratio of metabolites to parent drug in the blood is lower than after oral administration. In particular 4-hydroxypropranolol is not present after intravenous administration.
- o **Distribution:** Propranolol is absorbed from the circulation and is widely distributed throughout the body tissues.

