7.4 Appendix D. Medical assessment

Measures	Protocol and Key Questions

Example physical health assessment questions
	
Study physician will perform a full physical examination including, but not limited to: Neurological system, cardiovascular system, Respiratory system, gastrointestinal system
 
A 12-lead ECG will be performed
 
Lying and standing blood pressure, as an active standing test
 
 • Participant is to be placed in a supine position, • Lying blood pressure is to be taken after being positioned supine for at least 5 minutes • The participant is to transition to a standing position • Standing blood pressure is to be taken immediately, then after 1 minute of standing. 
A participant will be excluded if there is a reduction in systolic blood pressure by ≥ 20 mmHg; a reduction in diastolic blood pressure by ≥ 10 mmHg or a heart rate increase of ≥ 30 beats per minute
 
Heart rate variability using ECG rhythm strips.
 
Drug and alcohol screen
 
Significant medical history, past or present, including diagnosis, prognosis, and severity
 
Medication the participant has taken in the last 3 months, including current regular medications:
 
 • Name: • Dosage: • Units: • Start date: • End date: • Use: 
Basal systolic blood pressure (exclude if < 100 mm Hg)
 
Basal heart rate (exclude if < 50 bpm)
 
History of adverse reaction to a beta-blocker in the past (exclude if YES)
 
Currently using a drug/substance that can interact adversely with propranolol? (exclude if YES)
 
If this person pregnant or breastfeeding a child? (exclude if YES)
 
Is this participant using contraceptives? (YES/NO/N/A)
 
If yes, what type:
 
Does this person present with a medical contraindication to take propranolol (exclude if YES):
 
 • Chronic obstructive asthma and bronchopneumopathy • Uncontrolled heart failure • Cardiogenic shock • Second- and third-degree atrioventricular block not paired • Spastic angina • Unpaired ear sinus disease • Bradycardia • Raynaud's syndrome and peripheral arterial disorders • Untreated pheochromocytoma • Arterial hypotension • Hypersensitivity to propranolol • Antecedent anaphylactic reaction • Hypoglycemia predisposition • Orthostatic hypotension • Other: 
Taking this all into account, can this person receive propranolol? (YES/NO)
 
Dosage and prescription of propranolol
 
Participants height:
 
Determine the dosage using the table below:

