- Any serious unexpected suspected adverse reactions (SUSARs)
- Any implemented amendments to protocol
- Any new safety information regarding oral ketamine use in published or unpublished studies relevant to the trial protocol.

We will submit **annual** reports to the HREC regarding:

- The progress of the study
- Any proposed amendments to protocol
- The secure maintenance of records and research data, and compliance with ethical conduct
- Upon **closure of the study**, we will inform the ethics committee and submit a closure report.

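### The fifth 24–48 hour HREC reporting trigger in Appendix I names oral ketamine instead of propranolol; secondarily, two Appendix D exclusion lines are worded more narrowly than section 5.11

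*Protocol*

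**What the plan says.** **Reporting rule.** Section 5.6 says that standard operating procedures govern adverse events and adds: "Summary details of the SOP can be found in Appendix I". Appendix I then gives five items for HREC notice within 24–48 hours: serious adverse events, serious adverse drug reactions, SUSARs, implemented protocol amendments, and "Any new safety information regarding oral ketamine use in published or unpublished studies relevant to the trial protocol". A separate annual list follows in the same appendix.

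**Other rules on new information.** Section 5.5 states: "Discontinuation of parts of this study or the entire study will be considered if new information about reconsolidation therapy becomes known to the researchers". Appendix N, the informed-consent procedure, requires fresh consent when the risks or benefits of a treatment change.

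**Contraindications.** Section 5.11 says of propranolol that "it is contraindicated in patients with congestive heart failure", and of beta-blockers generally that they are "contraindicated in any patient with a history of bronchial asthma, airways obstruction or a tendency to bronchospasm". The checklist in Appendix D, under an instruction to exclude on a yes answer, has "Uncontrolled heart failure" and "Chronic obstructive asthma and bronchopneumopathy".

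**The concern.** A safety-reporting commitment is useful only if it names the right drug. Staff who follow Appendix I as printed would watch the ketamine literature, which has no bearing on this trial, and would find no instruction to tell the HREC promptly about a new external signal on propranolol. The HREC reviews the protocol text, so the error also sits in what it is asked to approve.

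The Appendix D wording matters because it touches the two reactions that section 5.11 ranks highest: "The most serious adverse reactions encountered are congestive heart failure and bronchospasm in susceptible patients". A screener working down the checklist line by line would not be stopped by compensated heart failure, or by past or non-chronic asthma.

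**Working it through.** No arithmetic applies to the main point. The check sets the texts side by side.

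**1. Is the drug name wrong?** Sections 4.2, 5.1 and 5.11 all give oral propranolol as the only study drug. Ketamine appears nowhere else in the protocol text at hand. The sentence is complete, so this is neither a redaction nor a gap from text extraction.

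**2. What does the error leave uncovered?** Take a new external safety report on propranolol and test it against each rule.

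| Rule | Does it require prompt HREC notice of the report? |
|---|---|
| Triggers 1–3 (serious events, serious drug reactions, SUSARs) | No. In-trial events are covered, but this is external information |
| Trigger 4 (implemented amendments) | Only if the report leads to an amendment that is implemented |
| Trigger 5 | No, as printed: it concerns ketamine |
| Annual list in Appendix I | No. It covers progress, proposed amendments, records and compliance, and closure |
| Section 5.5 | No. It says discontinuation will be considered |
| Appendix N | No. It concerns re-consent |

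What remains uncovered is external propranolol information that leads to no implemented amendment. One of five triggers is affected.

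**3. Are the Appendix D lines narrower?**

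| Condition | Section 5.11 | Appendix D line | Falls between the two |
|---|---|---|---|
| Heart failure | Congestive heart failure, unqualified | Only if uncontrolled | Controlled or compensated heart failure |
| Airways | Any history of asthma, any obstruction, any bronchospastic tendency | Chronic obstructive disease | Past or non-chronic asthma; tendency to bronchospasm |

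Both lines are narrower on their face. Two neighbouring lines are garbled: the one for sinus-node disease cannot be understood as printed, and the one for second- and third-degree AV block ends in a stray qualifier.

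**4. Is there cover from elsewhere?** Yes, for step 3. Section 5.2 excludes anyone with a propranolol contraindication in the study physician's judgement. The medical assessment in section 5.4 considers asthma and cardiac problems. The phone screener in Appendix E asks about asthma and heart disease. Appendix D itself adds a physical examination, a 12-lead ECG, past and present medical history, an open line for other contraindications, and a final yes/no decision. None of these touches the reporting rule in step 2.

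**The case against.** The strongest reply is that nothing here would mislead a competent team. Appendix I only summarises an operating procedure that is not shown and may name the right drug. Events in participants are fully reportable. Appendix D is headed as example questions, its neighbouring lines read like translation slips, and the asthma line may be another slip rather than a deliberate restriction. Section 5.7 even cites asthma as an exclusion, so the intent is plain.

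Most of this stands for Appendix D, and it is why that part is secondary. It does not rescue the reporting trigger: the protocol's own text names the wrong drug, and no other printed rule fills the gap.

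Three stronger readings are tempting, and the documents do not support them.

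- A reader might infer that the protocol has no rule for new treatment information other than section 5.5. Appendix N also responds to changed risks, and an implemented amendment is itself a 24–48 hour item.
- A reader might infer that, with five of the six doses taken at home (6 − 1 = 5), screening is the main safeguard for those doses. Section 5.1 puts the first dose under a nurse's supervision with the physician on site. Later doses are taken 60 minutes before sessions held on site, and section 5.11 puts peak blood level at 1 to 3 hours, so participants are due with staff as that window opens. Section 5.5 withdraws participants after an adverse reaction.
- A reader might infer from section 5.7 that diabetes is an exclusion missing from section 5.2 and Appendix D. That rests on one illustrative mention. Section 5.11 contraindicates proneness to hypoglycaemia, and Appendix D already lists that.

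**Conclusion.** The reporting trigger is wrong as written and should be corrected. Its reach is limited to prompt HREC notice of external propranolol safety information that leads to no implemented amendment. This assumes that Appendix I is applied literally; the underlying operating procedure may already say the right thing, but it cannot be checked here.

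The two Appendix D lines are narrower than section 5.11, but the documents do not support a claim that contraindicated patients would be enrolled. The physician-judged criterion governs, and several independent screening steps ask about the same conditions.

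Overall this is a minor safety-text correction. It has no bearing on the endpoint, the sample size or the analysis.

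**What to change.** - **Appendix I:** in the fifth 24–48 hour item, replace oral ketamine with propranolol. Check the underlying operating procedure for the same slip.
- **Appendix D, heart failure:** drop the restriction to uncontrolled disease, so that the line reads congestive heart failure.
- **Appendix D, airways:** reword the line to cover any history of bronchial asthma, any airways obstruction and any tendency to bronchospasm, as section 5.11 does.
- **Appendix D, garbled lines:** at the same time, restate them as sick sinus syndrome and second- or third-degree AV block.

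The cost is one drug name and four checklist lines, which can go into the next HREC amendment. Visits, sample size and analysis are unchanged.

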7.12 Appendix K. Recruitment Materials

Recruitment Email to Referral Network

Subject: Invitation to Participate in a Novel PTSD Treatment Study at UniSC's Thompson Institute

Dear [GP, Psychologist, Psychiatrist, Other Mental Health Professionals],

I hope this message finds you well. I am writing to inform you of an exciting new research study being conducted at the **National PTSD Research Centre** within **UniSC's Thompson Institute**. The Centre is focused on providing solutions for the 1.4 million Australians living with post-traumatic stress disorder (PTSD) and the many others impacted by psychological trauma.

We are currently recruiting participants for a study investigating an emerging treatment for PTSD, developed by the Thompson Institute's Director, **[name]**. This novel treatment, known as **Reconsolidation Therapy**, has significant potential to improve lives by addressing the neurobiological mechanisms behind the brain's reconsolidation of traumatic memories.

Study Details:

- **Participants:** Adults aged 18 and over, with diagnosed or suspected PTSD
- **Duration:** A 6-week treatment intervention, with comprehensive assessments conducted before and after.
- **Intervention:** Reconsolidation therapy, which includes the use of a specific medication to temporarily make the brain more receptive to updating traumatic memories. The therapy itself is safe and non-invasive, and it doesn't alter consciousness.
- **Aims:**
 - o To determine if a 6-session course of reconsolidation blockade treatment (i.e., oral propranolol treatment combined with script-driven trauma recall) is efficacious in reducing PTSD symptom frequency and severity in adults.
 - o To examine the psychosocial, neurocognitive, neurobiological, neuroimaging and physiological effects of reconsolidation blockade treatment in adult participants with PTSD.
- **Eligibility:** A written referral from a medical professional is required for participation.
- **NOTE:** Participation in this study is not intended to replace existing treatment arrangements. Participants must have an active treating health team in place to be able to participate.

The study will be building on previous research on this topic and holds the potential to make a substantial difference in the lives of those affected by PTSD or trauma. If you have any patients who may benefit from this therapy, we encourage you to refer them to us.

For more information or to discuss the study in detail, please don't hesitate to contact us at [contact]. We look forward to collaborating with you in offering this innovative treatment option to those in need.

Kind regards

[name]

Manager, Clinical Programs

Thompson Institute National PTSD Research Centre

[name]

University of the Sunshine Coast

[contact]

[contact]

[contact] | usc.edu.au

Thompson
Institute

Exciting new PTSD treatment study

Are you or someone you know living with PTSD or the impacts of trauma? The National PTSD Research Centre at UniSC's Thompson Institute is recruiting participants for a research study investigating a new treatment for PTSD.

Led by [name], this study focuses on Reconsolidation Therapy—a treatment designed to help the brain update traumatic memories by reducing their emotional impact.

What's involved?

- **Participants:** Adults aged 18+ with diagnosed or suspected PTSD.
- **Duration:** A 6-week program with comprehensive assessments before and after.
- **The treatment:** Safe and non-invasive, it includes a medication to help your brain process and update trauma-related memories.

Why is this important? We are exploring how this novel therapy can reduce PTSD symptoms and improve the lives of those affected by trauma. Participants will be helping advance research that could change the future of PTSD treatment.

Interested in joining?

A written referral from a medical professional is required to participate.

For more info or to see if you're eligible, contact us today:

[name]
[contact]

Trusted.
Trailblazing.

University of the Sunshine Coast
CRICOS: 01895D | TEQSA PRV12082

Transforming lives through mental health research, training and treatment.

Social media post – Thompson Institute’s Social Media Accounts

Exciting New PTSD Treatment Study at UniSC’s Thompson Institute

Are you or someone you know living with PTSD or the impacts of trauma? The National PTSD Research Centre at UniSC’s Thompson Institute is recruiting participants for a research study investigating a new treatment for PTSD.

Led by [name], this study focuses on Reconsolidation Therapy—a treatment designed to help the brain update traumatic memories by reducing their emotional impact.

What’s involved?

- **Participants:** Adults aged 18+ with diagnosed or suspected PTSD.
- **Duration:** A 6-week program with comprehensive assessments before and after.
- **The treatment:** Safe and non-invasive, it includes a medication to help your brain process and update trauma-related memories.

Why is this important? We are exploring how this novel therapy can reduce PTSD symptoms and improve the lives of those affected by trauma. Participants will be helping advance research that could change the future of PTSD treatment.

Interested in joining the study? A written referral from a medical professional is required to participate.

For more info or to see if you’re eligible, contact us today at [contact].

Help us make a difference in PTSD treatment and share this post with someone who might benefit!

7.13 Appendix L. Risk Assessment Register

RISK REGISTER - Clinical Research Unit															
User Display Code & last updated	Risk Description - current	Risk - caused by	Risk - implications	Risk Category	Inherent Risk	Controls			Control Owner	Control Delegate	Residual Risk	Additional actions to be taken to mitigate Risk Treatment			
TI_06	Danger, injury or harm to research participant or client	Interventions administered to patients as part of a clinical trial or research study, faulty or poorly maintained equipment, inadequate processes, poorly trained staff, aggrieved participant or client, exposure to traumatic events or recollection of experiences from participants or clients	Patient experiences negative or unexpected health issues and side effects, physical or psychological harm/disruption or discontinuation in trial or study, reputational impacts, legal impacts.	People Risk	Moderate	Possible Medium	
 • UnISC ethics approval sought for all research studies • Informed written consent obtained prior to commencement of study • Screening is undertaken of all participants • Trained technicians operating MRI • Ongoing MRI maintenance with external contractors • Standard Operating Procedures and Guidelines developed and maintained by Program Lead and subject matter experts; followed by all staff. • Program specific processes have also been developed with review cycle in place • Staff are made aware of SOPs during induction and are supervised until competent • Ongoing training and professional development for clinicians and research staff • Swipe access to the building and 24/7 monitoring by SafeUnISC, 2 staff on site at all times with participants (including after hours) • Buzzer Alarms are fitted and in place and activated if there is any threat to staff or participant safety. Onsite safeUnISC staff respond during office hours with remote support provided by safeUnISC at Sippy Downs outside of normal working hours • UnISC EAP available for clinical debriefing sessions for staff • Debrief completed with all participants following Neurocognitive assessments to address any reported suicidality and/or distress observed or reported during the session • Suicide risk escalation protocol and Distress Management Protocols developed and applied as needed • TI has client feedback processes in place for all consumers to provide compliments or raise concerns • Research team sends reminders to participants in the lead up to assessment days so that the participant can prepare • Call bell system with patient call button and staff assist button fitted and operational. SOP for staff re responses • Staff trained in clinical research practices, de-escalation skills, trauma-informed care, working alone and in isolation • All staff have completed GCP training • All clinical and neurophysiology assessments will be conducted within business hours, when clinical staff are accessible • Critical support for RA's, to assist in managing participants and debriefing following assessments (when necessary) • Screening is undertaken of all participants • Standard Operating Procedures developed and maintained by Program Lead and subject matter experts; followed by all staff. • Program specific processes have also been developed with review cycle in place • Staff are made aware of SOPs during induction and are supervised until competent • Ongoing training and professional development for clinicians and research staff • Swipe access to the building and 24/7 monitoring by SafeUnISC, 2 staff on site at all times with participants (including after hours) • Buzzer Alarms are activated if there is any threat to staff or participant safety. Onsite safeUnISC staff respond during office hours with remote support provided by safeUnISC at Sippy Downs outside of normal working hours • UnISC EAP available for clinical debriefing sessions for staff 	Administrative	Effective	Director, Thompson Institute	Manager, Clinical Programs	Minor	Unlikely	Low	
TI_07	Danger, injury or harm to staff member, student or visitor	Staff member, student or visitor is injured by faulty equipment, other staff member, aggrieved participant or visitor	Individual experiences negative or unexpected health issues and side effects, physical or psychological harm/disruption or discontinuation in trial or study, reputational impacts, legal impacts.	People Risk	Moderate	Possible Medium	
 • Screening is undertaken of all participants • Standard Operating Procedures developed and maintained by Program Lead and subject matter experts; followed by all staff. • Program specific processes have also been developed with review cycle in place • Staff are made aware of SOPs during induction and are supervised until competent • Ongoing training and professional development for clinicians and research staff • Swipe access to the building and 24/7 monitoring by SafeUnISC, 2 staff on site at all times with participants (including after hours) • Buzzer Alarms are activated if there is any threat to staff or participant safety. Onsite safeUnISC staff respond during office hours with remote support provided by safeUnISC at Sippy Downs outside of normal working hours • UnISC EAP available for clinical debriefing sessions for staff 	Administrative	Effective	Director, Thompson Institute	Manager, Clinical Programs	Minor	Unlikely	Low	
TI_01	Breach of personal information	Accidental or willing breaches of private information, physical loss of data/records, cyber/network attack.	Privacy penalties, participant exposure, costs relating to remedying and notification of potentially affected parties, potential media attention, reputational impacts.	Regulatory and Compliance Risk	Moderate	Unlikely Medium	
 • Hard copies of personal data is stored and locked away in cabinets in rooms with access restricted to key staff who are authorised to access the records. • Electronic records are stored in RealTime and the R drive with access restricted to authorised staff. Once data is entered into the system, it is de-identified and coded. Identifiable electronic data is only accessible to authorised staff with restricted access in accordance with the data management plan • Staff have individual logins to electronic participant software systems • Participant consent forms explain the limits of confidentiality a participant is at risk of harm of self or others • Ongoing privacy training and professional development for clinicians and research staff • UnISC Policies and Procedures are in place in the event of a data breach. This includes, but is not limited to, recall of email, support from UnISC to include notification management and staff discussions. • UnISC has Research Data Management - Procedures in place • UnISC Information and Records Management Policy & Procedures in place. • UnISC Responsible Research Conduct - Academic Policy • UnISC Disposal of Digitised Records - Procedures. • UnISC Policies & Procedures include staff expectations in the management of the personal information of participants and clients • UnISC has mandatory training at induction with ongoing training and professional development for clinicians and research staff • Minimal identifying information is included in emails and does not include any sensitive information about the participant 	Administrative	Effective	Director, Thompson Institute	Manager, Clinical Programs	Moderate	Rare	Low	
TI_08	Loss or damage to data and/or samples	Loss of power or service disruption, faulty or poorly maintained equipment, critical incidents such as fire or flooding, procedures not followed.	Damage to equipment, project deliverables not met, leakage of helium into environment, damage to MRI, financial loss, reputational impacts.	Research Risk	Major	Possible High	
 • Data will be stored in the cloud/data will be backed up with secure process. Dual location of data storage will minimise risk of loss of data. Software selected to minimise loss of data due to technical failure (i.e. multiple save points or offline program/not dependent on power or internet). • Data management plan in place with UnISC that is reviewed on an annual basis • Power is maintained to the MRI at all times via backup generator • Trained technicians operating MRI • Ongoing MRI maintenance with external contractors • Standard Operating Procedures developed and maintained by Program Lead and subject matter experts; followed by all staff • Staff are made aware of SOPs during induction and are supervised until competent • SOPs are reviewed annually by Manager, Clinical Programs and relevant Thompson Institute Governance Committee/s • Ongoing training and professional development for clinicians and research staff 	Administrative	Effective	Director, Thompson Institute	Manager, Clinical Programs	Moderate	Possible	Medium	UnISC Cybersecurity Risk acknowledged and managed by the Thompson Institute
TI_02	Breach of compliance obligations.	Not identifying a new regulation or a change to existing legislation, poor control to comply with current legislation.	Penalty/s, legal action. Breach may also require HREC implications and further funding to Clinical Research Programs	Regulatory and Compliance Risk	Major	Possible High	
 • Regular liaison with UnISC on compliance with University expectations. • Annual reporting to HREC or as required • Restricted access to drug safe, and restricted access to drug room. • Restricted access to TMS machine. • Maintenance of drug register and audits of medication management procedures in accordance with Medicines and Poisons Act 2019 (Queensland) and Medicines and Poisons Regulation 2021 (Queensland). • For participants that indicate suicidal intent during an assessment (e.g. telephone call, in person), study protocol procedures and Thompson Institute Escalation of Care Guidelines will be followed and in consultation with the supervising clinician. Actions may include calling an ambulance in the case of an emergency. • Clinicians delivering treatment are registered through their respective registration board that is governed by AHPRA • Thompson Institute has an established Governance Committees that will retain oversight of clinical and research governance and compliance with legislation and guidelines. • The TI NPRC has developed a recruitment plan prior to commencing operation and will amend this accordingly over the duration of the project. • Projections and actuals spreadsheet commenced and updated by research team RAs to monitor actual recruitment and staffing needs • Adjust strategies if baseline drops below required intake per month • Engage and develop strong working relationships with stakeholders for recruitment and study related processes (e.g. GPs, Psychology practices, PHN commissioned services, mental health peer support groups) • Ensure participants understand the time commitment and expectations involved in participation, as well as any reimbursements/petrol vouchers. • Offer appointment SMS reminders if participants consent to this • When flexibility in the project timeline allow for expected processing timelines of external bodies and/or resubmissions (e.g. ethics or governance). • Allow flexibility within the protocol and approval bodies permits. • Ensure time and resources are delegated to ensure they are completed in timely manner. • Extensions requested in a timely manner if required. • Ensure adequate staffing is available to meet the intake/recruitment requirements. • Shared resources with other TI programs to meet intake/recruitment requirements. • Surveying of the local population and stakeholder networks to ensure appropriate intake/recruitment can be achieved. 	Administrative	Effective	Director, Thompson Institute	Manager, Clinical Programs	Moderate	Rare	Medium	
RC_01	Inability to recruit a suitable amount and right demographic of research participants	Delays in relevant approvals (i.e. ethics, governance, contractor, other research partners) or barriers to participation	Unable to meet project outcomes, inability to provide quality research that can be published in a well-respected journal. Further implications will limit future funding for ongoing research and will impact on the TI and UnISC reputation. Perception of inappropriate use of public or donated funds. Staff and students will decrease job satisfaction and may not be gainfully employed. Loss of PhD Students, inability to gain reputational impact factors with regards to specialisations in Mental Health Research	Research Risk	Major	Possible High	
 • The TI NPRC has developed a recruitment plan prior to commencing operation and will amend this accordingly over the duration of the project. • Projections and actuals spreadsheet commenced and updated by research team RAs to monitor actual recruitment and staffing needs • Adjust strategies if baseline drops below required intake per month • Engage and develop strong working relationships with stakeholders for recruitment and study related processes (e.g. GPs, Psychology practices, PHN commissioned services, mental health peer support groups) • Ensure participants understand the time commitment and expectations involved in participation, as well as any reimbursements/petrol vouchers. • Offer appointment SMS reminders if participants consent to this • When flexibility in the project timeline allow for expected processing timelines of external bodies and/or resubmissions (e.g. ethics or governance). • Allow flexibility within the protocol and approval bodies permits. • Ensure time and resources are delegated to ensure they are completed in timely manner. • Extensions requested in a timely manner if required. • Ensure adequate staffing is available to meet the intake/recruitment requirements. • Shared resources with other TI programs to meet intake/recruitment requirements. • Surveying of the local population and stakeholder networks to ensure appropriate intake/recruitment can be achieved. 	Administrative	Effective	Director, Thompson Institute	Manager, Clinical Programs	Moderate	Possible	Medium	

